13.4 Analysis of Exploratory Endpoints

We will assess the effect of AZD1775 on DNA damage response based on immunofluorescence analysis of markers of DNA damage, Rad51, pNbs1, and γ H2AX in tumor biopsies, pTyr15-Cdk, and caspase 3 in CTCs as a marker of apoptosis.

13.5 Reporting and Exclusions

- **13.5.1** Evaluation of toxicity All patients will be evaluable for toxicity from the time of their first treatment with study agents.
- 13.5.2 Evaluation of response All patients included in the study will be assessed for response to treatment, even if there are major protocol treatment deviations or if they are ineligible. Each patient will be assigned one of the following categories: 1) complete response, 2) partial response, 3) stable disease, 4) progressive disease, 5) early death from malignant disease, 6) early death from toxicity, 7) early death because of other cause, or 9) unknown (not assessable, insufficient data). [Note: By arbitrary convention, category 9 usually designates the "unknown" status of any type of data in a clinical database.]

All of the patients who met the eligibility criteria (with the possible exception of those who received no study medication) will be included in the main analysis of the response rate. Patients in response categories 4-9 will be considered to have a treatment failure (disease progression). Thus, an incorrect treatment schedule or drug administration does not result in exclusion from the analysis of the response rate. Precise definitions for categories 4-9 will be protocol specific.

All conclusions will be based on all eligible patients. Sub-analyses may then be performed on the basis of a subset of patients, excluding those for whom major protocol deviations have been identified (e.g., early death due to other reasons, early discontinuation of treatment, major protocol violations, etc.). However, these sub-analyses may not serve as the basis for drawing conclusions concerning treatment efficacy, and the reasons for excluding patients from the analysis will be clearly reported. The 95% confidence intervals will also be provided.

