11.1.1 Definitions

Evaluable for toxicity: All patients will be evaluable for toxicity from the time of their first treatment with AZD1775.

Evaluable for objective response: Only those patients who have measurable disease present at baseline, have received at least one cycle of therapy, and have had their disease re-evaluated will be considered evaluable for response. These patients will have their response classified according to the definitions stated below. (Note: Patients who exhibit objective disease progression prior to the end of cycle 1 will also be considered evaluable.)

Evaluable Non-Target Disease Response: Patients who have lesions present at baseline that are evaluable but do not meet the definitions of measurable disease, have received at least one cycle of therapy, and have had their disease re-evaluated will be considered evaluable for non-target disease. The response assessment is based on the presence, absence, or unequivocal progression of the lesions.

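### Does the response coding in section 13.5.2 distort the reported antitumor activity?

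*Combined protocol and SAP*

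**What the plan says.** Section 13.5.2 starts from a single code per patient: "Each patient will be assigned one of the following categories". The codes are complete response, partial response, stable disease, progressive disease, early death from malignant disease, and then "6) early death from toxicity, 7) early death because of other cause, or 9) unknown (not assessable, insufficient data". Everything from code 4 upward is pooled: "Patients in response categories 4-9 will be considered to have a treatment failure (disease progression". The same section adds "Precise definitions for categories 4-9 will be protocol specific".

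On the analysis set, eligible patients, with a possible exception for those never dosed, "will be included in the main analysis of the response rate". Analyses that leave out patients with major deviations are allowed, but "these sub-analyses may not serve as the basis for drawing conclusions concerning treatment efficacy". Conclusions rest on all eligible patients, and 95% confidence intervals are to be given.

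Section 11.1.1 defines two evaluable groups. Objective response applies to "Only those patients who have measurable disease present at baseline, have received at least one cycle of therapy, and have had their disease re-evaluated", plus patients with objective progression before the end of cycle 1. A second group covers "Patients who have lesions present at baseline that are evaluable but do not meet the definitions of measurable disease". Section 3.1.2 admits evaluable-only disease in escalation. For patients without measurable lesions, section 11.3.3 uses the outcome Non-CR/non-PD and advises against calling it stable disease.

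**The concern.** Four things look wrong when these sections are read together.

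1. An assessed, non-progressing patient with only non-target lesions has no code in 13.5.2. Code 3 goes against the advice in 11.3.3. Code 9 is meant for patients who could not be assessed, and the pooling sentence then makes it progression.
2. The pooling sentence attaches the word progression to toxic deaths (6), deaths from other causes (7) and unassessable patients (9).
3. Definitions are promised for codes 4 to 9. Progression is defined in 11.3, and code 9 explains itself in brackets. Codes 5 to 7 are not defined, and neither is the meaning of early.
4. The main response set in 13.5.2 is wider than the objective-response group in 11.1.1, and no sentence connects them.

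Antitumor activity is the only secondary objective. If the coding changed the response rate, or if toxic deaths disappeared into a progression count, the reader would be misinformed about activity and possibly about safety.

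**Working it through.** The plan gives no response rate, threshold or sample size that depends on this coding, so there is no planned figure to reproduce. The check is whether any coding choice alters an analysis the plan actually specifies.

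**Inputs from the documents.** Section 2.3: 18 patients enrolled on Arm A and 2 confirmed partial responses at Amendment G. Section 13.3: accrual ceiling of 72, and a BRCA expansion arm of 6. Section 13.5.2: all-eligible denominator and 95% intervals. **Assumed:** that all 18 are eligible and treated; that 1 to 3 of them are Non-CR/non-PD; and that 0 to 6 fall outside the 11.1.1 objective-response group. The documents give none of these counts.

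**Step 1: follow each disputed patient into the main rate.**

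| Patient | Possible code | In denominator | In CR+PR |
|---|---|---|---|
| Non-CR/non-PD | 3 or 9 | yes | no |
| Toxic death | 6 | yes | no |
| Death from other cause | 7 | yes | no |
| Not assessable | 9 | yes | no |

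No row changes the numerator or the denominator.

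**Step 2: the rate and its interval.** The exact (Clopper-Pearson) limits for x responders among n are the 0.025 quantile of Beta(x, n − x + 1) and the 0.975 quantile of Beta(x + 1, n − x). With x = 2 and n = 18, the rate is 2/18 = 11.1%, with limits 1.4% and 34.7%. This holds under every coding in the table.

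**Step 3: what does move.** Each recoded patient shifts the stable-disease or progression tally by 1/18 = 5.6 points. Three patients shift it by 3/18 = 16.7 points. Pooled at the accrual ceiling, one patient is 1/72 = 1.4 points; in the BRCA arm, one is 1/6 = 16.7 points. The BRCA arm requires measurable disease (3.1.2), so only the labelling question can arise there.

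**Step 4: is a moved tally used anywhere?** Section 11.4 ends response duration at objectively documented progression, and ends stable-disease duration when the progression criteria are met. Neither uses the pooled failure label. The plan specifies no progression-free survival, disease-control rate or progression rate. Each patient keeps an individual code, so a toxic death remains visible as code 6. It is also captured in the toxicity evaluation (13.5.1) and the expedited reporting of section 7.3.

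**Step 5: the undefined term early.** Codes 5, 6 and 7 are all failures, so moving a patient among them, or between them and code 4 or 9, leaves the rate alone. A patient who responded and later died keeps the response, because 11.3.3 takes the best response recorded from the start of treatment until progression.

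**Step 6: the two analysis sets.** If the 11.1.1 group were the denominator, the rate would be 2/16 = 12.5% (1.6% to 38.3%) with 2 patients outside it, 2/15 = 13.3% (1.7% to 40.5%) with 3, and 2/12 = 16.7% (2.1% to 48.4%) with 6. Section 13.5.2 rules that out, because it names all eligible patients as the basis of the main rate and of every conclusion. Section 11.1.1 says whose response can be classified against the criteria. It does not say that the rate is computed on that group. Patients who cannot be classified go to code 9 and stay in the denominator.

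**The case for a change.** The best argument for a change is that the words are wrong as they stand and cheap to mend. Elsewhere the protocol treats progression as an objective finding, so calling a toxic death progression is inconsistent. Two careful coders could place the same Non-CR/non-PD patient in stable disease or in failure. The label might also spread: CTC changes (2.4.1) and the Immunoscore (2.4.3) are to be related to response, with CTCs also related to progression, and sequenced specimens (9.3) keep only brief annotation such as response to the drug. The BRCA arm is meant to inform later patient selection.

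Part of this stands. The list does lack a Non-CR/non-PD entry, and the bracketed word is loose for codes 6, 7 and 9. The wider argument does not. The pooling sentence sits among sentences about who counts in the response rate, and its purpose is to keep difficult patients in as failures, which is an acceptable conservative convention. The exploratory work is not tied to the pooled label, and an analyst would use the individual code or the RECIST outcome. Section 11.3.3 states a preference about stable disease, on the ground that some trials use it as an efficacy endpoint; this trial names no such endpoint. The BRCA arm cannot contain a Non-CR/non-PD patient.

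**Conclusion.** No change to the plan follows. What remains is one missing entry in a coding list and one imprecise word in brackets. The planned response rate and its 95% interval are identical with or without a correction: 2/18 = 11.1% (1.4% to 34.7%) in the Arm A illustration. The missing definitions of codes 5 to 7 and the missing cross-reference to 11.1.1 do not affect that analysis either.

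The possible movement of 5.6 points per patient in the stable-disease or progression tally depends on patient counts that the documents do not give, and it affects summaries the plan does not specify. Response is descriptive here, with no test or threshold, and no dose decision depends on it. An analyst can fill the gap without instruction: report non-measurable patients with the 11.3.3 table, show codes 4 to 9 individually, and count them all as non-responders.

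This conclusion assumes that the all-eligible rate stays the basis for statements about activity. If a progression rate or disease-control rate were later added, the coding would need to be settled first.

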14 HUMAN SUBJECTS PROTECTIONS

14.1 Justification for Subject Selection

This study will be open to all individuals regardless of gender, ethnicity, or race, provided that the aforementioned inclusion and exclusion criteria are met. Patients for this study will be recruited through internal referral, our physician referral base, and through various cancer information hotlines (i.e., Clinical Studies Support Center, [name]). To date, there is no information that suggests that differences in drug metabolism or effect on tumor would be expected in one ethnic group compared to another. Efforts will be made to extend accrual to each representative population, but a balance must be struck between participant safety considerations and limitations on the number of individuals exposed to potentially ineffective treatments on the one hand and the need to explore racial/ethnic aspects of clinical research on the other hand. If differences in outcome that correlate to ethnic identity are noted, a follow-up study may be written to investigate those differences more fully.

Due to lack of knowledge of the effects of AZD1775 on the fetus or infants, as well as the possibility of teratogenic effects, pregnant and nursing women will be excluded from this trial. Patients with unstable or serious medical conditions are excluded due to the possibility that AZD1775 may worsen their condition and the likelihood that the underlying condition may obscure the attribution of adverse events to AZD1775. HIV-positive patients on combination antiretroviral therapy are excluded from the study because of possible PK interactions with AZD1775.

14.1.1 Participation of Children

This study includes patients 18 years of age and older. Because insufficient dosing or adverse event data are currently available on the use of AZD1775 in patients <18 years of age, children are excluded from this study, but may be eligible for future pediatric trials. Studies will be performed in patients <18 years of age when it is appropriate to do so.

14.2 Evaluation of Benefits and Risks/Discomforts

There may or may not be any clinical benefit to a patient from participation in this trial. Their participation will benefit future cancer patients. Potential risks include the possible occurrence of any of a range of side effects that are listed in the consent document. The procedure for protecting against or minimizing risks will be to medically evaluate patients as described in Sections 5 and 6. Although no compensation is available, any injury will be fully evaluated and treated in keeping with the benefits or care to which participants are entitled under applicable regulations.

All patients > 18 years old will be offered the opportunity to assign a substitute decision maker on the "NIH Advance Directive for Health Care and Medical Research Participation" form, so that another person can make decisions about their medical care if they become incapacitated or cognitively impaired. The process for determining whether

adults who lose capacity to give consent may continue participation in this trial, with its heavy reliance on non-therapeutic endpoints and collection of research samples, will be on a case-by case basis and will include consultation among the substitute decision maker, protocol PI, and patient's physician regarding the health of the patient and likelihood of benefit from continued treatment.

14.3 Consent and Assent Process and Documentation

An associate or principal investigator on the trial will inform patients of the purpose, alternatives, drug administration plan, research objectives, and follow-up of this trial. The patient will be provided an IRB-approved consent for review and signature and his/her questions will be answered. After a decision is made to enroll into the study, a signature will be obtained from the patient. The original signed consent goes to Medical Records; a copy will be placed in the research record.

All patients must have a signed informed consent form and an on-study (confirmation of eligibility) form filled out and signed by a participating investigator before entering on study.

14.4 Procedure for Protecting Against or Minimizing Any Potential Risks

All care will be taken to minimize side effects, but they can be unpredictable in nature and severity. This study may involve risks to patients, which are currently unforeseeable. All patients will be monitored for side effects from taking study medication. This research represents a greater than minimal risk to participants, but presents the prospect of direct benefit to individual subjects.

The research component of this study required to obtain up to 3 CT tumor biopsies confers radiation exposure at an effective dose of 2.4 rem. This dose is below NIH RSC guidelines and represents a slightly greater than minimal risk to patients.

	In bed >50% of the time. Capable of only limited self-	40	Disabled, requires special care and assistance.	
3	care, confined to bed or chair more than 50% of waking hours.	30	Severely disabled, hospitalization indicated. Death not imminent.	
	100% bedridden. Completely disabled. Cannot carry on any	20	Very sick, hospitalization indicated. Death not imminent.	
	self-care. Totally confined to bed or chair.	10	Moribund, fatal processes progressing rapidly.	
5	Dead.	0	Dead.	

1. APPENDIX A: PERFORMANCE STATUS CRITERIA

National Cancer Institute Dev	elopmental Therapeu	tics Program	NSC : D - 754352/2	Units :Molar	SSPL :U49P	EXP. ID :1101NS86	
	Mean Graphs		Report Date :February 0	1, 2012	Test Date :January 18, 2011		
Panel/Cell Line	Log 10GISD	GI50	Log 10 TGI	TGI	Log ₁₀ LC50 L	C50	
Leukemia CCRF-CEM HL-69(TB) MCCT-4 RPMI-8226 SR Non-Small Cell Lung Cancer	-6.67 -6.57 -6.50 -6.49 -6.85 -6.63	_	-4.88 -5.87 -4.54 -5.30 -5.95	Ł	> 400 415 > 4400 > 400 > 400 > 400		
A549/ATCC EKXX HSB-52 NCI-H226 NCI-H322M NCI-H460 NCI-H522 Colon Cancer	-6.727 -6.257 -6.2651 -6.158 -6.558 -6.379 -6.75		4.89 4.61 4.61 4.89 4.89 5.77 > 4.89 -6.22	Ξ	> -4.00 -4.01 > -4.00 > -4.00 > -4.00 > -4.00 > -4.00 4.00 4.00 4.00		
A02-9.205 HCT-116 HCT-15 HT29 KM12 SW-620 CNS Canper	-659 -6.49 -6.12 -6.70 -6.52 -6.47	-	-5.86 -4.97 > -4.00 -6.30 -5.79 -5.00	F	+ 464 + 426 + 426 - 426 - 426 - 426 - 420 + 420 - 420 - 420 - 420		
SF-588 SF-539 SNB-19 SNB-75 U251 Metanoma	-5.84 -6.32 -6.67 -5.78 -6.72 -6.17		-4.38 -4.77 -5.42 -4.87 -4.80	-	> -4.00 +4.09 +4.18 > -4.00 -4.31 > -4.01		
MALME-3M M14 MDA-MB-435 SK-MEL-2 SK-MEL-28 SK-MEL-28 UACC-52 UACC-52 Ovariar Caper	0538 05589 05589 05589 05433 05443 0545 0545 055 055 055 055 055 055 055 0		-0.40 -4.64 -6.00 -6.23 -6.30 -4.72 -6.18 -4.72 -4.67		> 4.00 4.15 4.41 4.522 4.522 4.52 4.79 4.79 4.70 4.10		
IGROV1 OVCAR-3 OVCAR-5 OVCAR-5 NCIADE-RES SK-OV2 Renal Cancer	-6.78 -6.62 -6.20 -6.35 -5.43 -5.56	4	-4.34 -6.01 > -4.00 -5.51 -4.99		> -4.00 -4.82 > -4.00 -4.28 > -4.08	_	
766-0 A498 ACHN CAKI-1 BXF283 TK-10 UO-31 Prostate Cancer	-6.38 -7.47 -7.05 -6.55 -6.55 -6.84 -6.36	Ē	-4.92 -6.73 > -4.00 -4.76 -4.76 -6.70 -4.76 -4.82 -4.82	F	4.36 4.85 - 4.00 - 4.04 - 5.00 - 4.31 - 4.16	 	
PC-3 DU-145	-5.79 -6.05	-	-4.37 -4.69		> -4.00 > -4.00		
MDA-MB-231/ATCC HS 578T BT-549 T-47D MDA-MB-468	-6.53 -5.99 -6.01 -6.38 -6.64 -6.74	1	4.82 4.36 -4.00 -5.14 -5.98	_	> -4.00 > -4.00 > -4.00 > -4.00 -5.16		
MID Detta Range	-6.33 1.14 2.04		-5.07 1.66 2.73		-4.23 1.14 1.37 -3 -2 -1	0 1 2 3	

2. APPENDIX B: AZD1775 (MK-1775) Activity in the NCI-60 Cell Line Screen

Г

4. APPENDIX D: PATIENT'S MEDICATION DIARY - AZD1775

Arm A DL1 and DL-1 of AZD1775 only

INSTRUCTIONS

1. Complete one form for each cycle of treatment.

2. Swallow each capsule whole with a full glass of water either 2 hours before or 2 hours after a meal. Do not chew or open the capsules. If capsule is broken and the powder of the capsules gets on skin, wash the exposed area with as much water as necessary. Inform investigator or nurse if that occurs.

3. Record the date and time you took the capsule. The boxes in gray reflect times when you should **not** be taking drug.

4. If you have any comments or notice any side effects, please record them in the Comments column.

5. Please bring this form and your bottle of AZD1775 when you return for your Day 21 appointment.

6. In case of errors, please place a single slash mark through the error and initial it. Please do not white out any error or scribble it out with ink. Please do not write the correct information directly over the error, but on a separate line next to the error.

Today's Date _____

Cycle #____ Dose____mg x5/week

 Patient Name______(initials acceptable)

Patient Study ID _____

DL1 and DL-1 of AZD1775 only

Day	Date	Time	of dose	Number	of Capsule	es Taken	Comments
		AM	PM	25 mg	100 mg	200 mg	
1					Î		
2							
3							
4							
5							
6							
7							
8							
9							
10					6 6		
11							
12					5 		
13							
14							
15							
16							
17							
18							
19					2		
20					£		
21							

Patient's signature: _________________________84

APPENDIX D - PATIENT'S MEDICATION DIARY - AZD1775

Arm A DL2 of AZD1775 and Higher

INSTRUCTIONS

1. Complete one form for each cycle of treatment.

2. Swallow each capsule whole with a full glass of water either 2 hours before or 2 hours after a meal. Do not chew or open the capsules. If capsule is broken and the powder of the capsules gets on skin, wash the exposed area with as much water as necessary. Inform investigator or nurse if that occurs.

3. Record the date and time you took the capsule. The boxes in gray reflect times when you should **not** be taking drug.

4. If you have any comments or notice any side effects, please record them in the Comments column.

5. Please bring this form and your bottle of AZD1775 when you return for your Day 21 appointment.

6. In case of errors, please place a single slash mark through the error and initial it. Please do not white out any error or scribble it out with ink. Please do not write the correct information directly over the error, but on a separate line next to the error.

Today's Date _____

Cycle # Dose 225 mg x 10 doses/2 weeks

 Patient Name______ (initials acceptable)

Patient Study ID _____

DL2 of AZD1775 and Higher

Day	Date	Time of	of dose	Number	of Capsule	es Taken	Comments
		AM	PM	25 mg	100 mg	200 mg	
1		0			3 5		
2		0 2			8 8		
3		8			a		
4					9		
5					×		
6							
7							
8							
9							
10							
11					÷		
12							
13							
14							
15							
16							
17							
18							
19							
20							
21							

Patient's signature:

APPENDIX D - PATIENT'S MEDICATION DIARY - AZD1775

Arm B

INSTRUCTIONS

- 1. Complete one form for each cycle of treatment.
- 2. Swallow each capsule whole with a full glass of water either 2 hours before or 2 hours after a meal. Do not chew or open the capsules. If capsule is broken and the powder of the capsules gets on skin, wash the exposed area with as much water as necessary. Inform investigator or nurse if that occurs.
- 3. Record the date and time you took the capsule. The boxes in gray reflect times when you should **not** be taking drug.
- 4. If you have any comments or notice any side effects, please record them in the Comments column.
- 5. Please bring this form and your bottle of AZD1775 when you return for your Day 21 appointment.

6. In case of errors, please place a single slash mark through the error and initial it. Please do not white out any error or scribble it out with ink. Please do not write the correct information directly over the error, but on a separate line next to the error.

Today's Date _____

Cycle #

Patient Name	(initials acceptable)
--------------	-----------------------

Patient Study ID _____

Arm B - AZD1775

Day	Date	Time of dose	Number	of Capsul	les Taken	Comments
	2	8	25 mg	100 mg	200 mg	
1						
2						
3						
4						
5						
6						
7						
8	2					
9						
10						
11						
12						
13						
14						
15						
16						
17						
18						
19						
20						
21						

Patient's signature:

5. APPENDIX E: INFORMATION ON POSSIBLE INTERACTIONS WITH OTHER AGENTS FOR PATIENTS AND THEIR CAREGIVERS AND NON-STUDY HEALTH CARE TEAM

Information for Patients, Their Caregivers, and Non-Study Healthcare Team on Possible Interactions with Other Drugs and Herbal Supplements

The patient _______ is enrolled on a clinical trial using the experimental study drug AZD1775 (formerly known as MK-1775). This clinical trial is sponsored by the National Cancer Institute. This form is addressed to the patient, but includes important information for others who care for this patient.

These are the things that you as a prescriber need to know:

To the patient: Take this paper with you to your medical appointments and keep the attached information card in your wallet.

